# **4 JUSTIFICATION FOR THE DESIGN OF THE CLINICAL INVESTIGATION**

#### 4.1 SUMMARY OF NON-CLINICAL/PRECLINICAL STUDIES

Non-Clinical Section	Description/Test Results
Electrical Safety and Electromagnetic Compatibility	Electrical safety and EMC testing demonstrated compliance with IEC 60601-2- 10:2012, AMD1:2012; IEC 60601-1:2015, AMD1:2012; IEC 60601-1-11:2015, AMD1:2012; BS EN 60601-1:2006 + A12:2014, and IEC/EN 60529:2013.
Software	Software documentation and verification and validation testing was completed for the FW-200 software, which has Moderate Level of Concern.
Sterilization and Shelf-Life	The Fisher Wallace Stimulator, Model FW-200 is not provided sterile. Accelerated shelf-life testing has been completed and has validated a 5year shelf-life for the FW-200 as of 3/8/2022. Reference report #EMTS290227 via EMTS Lab Inc. Fisher Wallace plans to conduct a realtime shelf-life study to validate a 5-year shelf life.

The following testing has been completed:

Bench Performance Testing	
 
Bench performance testing was conducted as recommended in FDA's Special Controls for CES devices, including:
 
Waveform
 
Output mode
 
Pulse duration
 
Frequency
 
Train delivery
 
Maximum charge and energy
 
 Stress/wear testing was conducted to verify that the device thumbwheel and headband withstand use throughout the expected use life of the device. Passing results were achieved.

# 4.2 SUMMARY OF CLINICAL STUDIES

To examine the safety and effectiveness of the Fisher Wallace Stimulator, Model FW- 200, for treatment of major depressive disorder (MDD), a double-blind randomized controlled trial (RCT) was performed in a fully remote fashion during the COVID-19 pandemic. Subjects with either mild, moderate, or severe major depressive disorder were enrolled in the study. Throughout the treatment period, participants administered twice daily 20-minute treatments with either the active device or a sham device treatment. Participants were randomized into immediate or delayed treatment arms. In the immediate treatment arm, participants administered active treatment (20 minutes of clinical stimulation per treatment session) for 8 weeks. Participants in the delayed treatment arm received sham stimulation (two seconds of clinical stimulation and 19 minutes and 58 seconds of zero stimulation per treatment for the following 4 weeks.

Participants completed reports of compliance with treatment, as well as assessments of symptoms and side effects throughout the study, particularly at weeks 2, 4, and 8. Physician assessments were performed prerandomization and at 4 weeks.

The primary outcome measure was change in Beck Depression Inventory Second Edition (BDI-II) score from baseline to week 4 in immediate versus delayed treatment arms. The BDI-II is a widely used selfreported instrument to assess the severity of depression in adolescents and adults from different cultural groups and populations (Beck Depression Inventory-Second Edition | The National Child Traumatic Stress

Version 5.0 08-Jun-2022

Network, n.d.). Secondary outcome measures included: change in Hamilton Depression Rating Scale from baseline to week 4, change in BDI-II from baseline to week 2, change in BDI-II from week 4 to 8, change in Patient Health Questionnaire-8 from baseline to week 2 and week 4, as well as safety and tolerability as measured by Systematic Assessment for Treatment of Emergent Events (SAFTEE).

This study enrolled 275 participants with 137 participants in the Immediate Treatment arm and 138 participants in the Delayed Treatment arm. Of these, 83 participants in the Immediate Treatment arm and 78 participants receiving delayed treatment completed 4-week assessments.

Table 1 provides the percentages of side effects experienced by subjects in both treatment arms at Week 4. Table 2 displays the percentages of patient-reported side effects at Week 8. There were no reported serious adverse events. Overall, more adverse events were reported in the Delayed Treatment arm than the Immediate Treatment arm. Minor symptoms reported were similar in both groups with 13/34 symptoms on SAFTEE reported more frequently in the Immediate Treatment group and 21/34 symptoms reported more frequently by individuals in the Delayed Treatment arm.

Table 1: Side Effects Reported by Subjects at Week 4			
	Immediate Treatment	Delayed Treatment	Total
Have you felt weak?	14.0% (8/57)	15.1% (8/53)	14.5% (16/110)
Have you felt drugged or like a zombie?	3.5% (2/57)	5.7% (3/53)	4.5% (5/110)
Have you been sweating more than usual?	5.3% (3/57)	7.5% (4/53)	6.4% (7/110)
Have you felt tired during the day?	54.4% (31/57)	66.0% (35/53)	60.0% (66/110)
Have you had difficulty staying awake during the day?	22.8% (13/57)	30.2% (16/53)	26.4% (29/110)
Have you had difficulties waking up fresh in the morning?	56.1% (32/57)	62.3% (33/53)	59.1% (65/110)

CES-MDD FW-200-05

Have you gained weight?	21.1% (12/57)	18.9% (10/53)	20.0% (22/110)
	l		
Do you think some foods taste different/odd?	7.0% (4/57)	11.3% (6/53)	9.1% (10/110)
Have you felt more hungry than usual?	14.0% (8/57)	17.0% (9/53)	15.5% (17/110)
Have you been more thirsty than usual?	24.6% (14/57)	22.6% (12/53)	23.6% (26/110)
Have your stools been hard or difficult to pass?	15.8% (9/57)	20.8% (11/53)	18.2% (20/110)
Have you needed to go to the toilet often?	24.6% (14/57)	17.0% (9/53)	20.9% (23/110)
Has your skin been more sensitive to the sun?	0.0% (0/57)	0.0% (0/53)	0.0% (0/110)
Have you noticed any areas of darker skin?	0.0% (0/57)	3.8% (2/53)	1.8% (2/110)
Are you experiencing any skin irritation where you place the Fisher Wallace device?	7.0% (4/57)	3.8% (2/53)	5.5% (6/110)
Do you have diabetes?	3.5% (2/57)	5.7% (3/53)	4.5% (5/110)
Have you been told that your blood sugar levels are high?	8.8% (5/57)	15.1% (8/53)	11.8% (13/110)
Have you noticed a change in your blood sugar levels?	0.0% (0/57)	0.0% (0/53)	0.0% (0/110)
Has your vision been blurry?	8.8% (5/57)	15.1% (8/53)	11.8% (13/110)
Have your eyes felt dry and gritty?	15.8% (9/57)	24.5% (13/53)	20.0% (22/110)

Are you experiencing any unusual eyestrain or headaches?	22.8% (13/57)	17.0% (9/53)	20.0% (22/110)
Have you found that your words dont come out clearly?	7.0% (4/57)	3.8% (2/53)	5.5% (6/110)
Have you found it difficult to swallow?	1.8% (1/57)	1.9% (1/53)	1.8% (2/110)
Have you felt anxious?	49.1% (28/57)	34.0% (18/53)	41.8% (46/110)
Have you felt agitated?	33.3% (19/57)	26.4% (14/53)	30.0% (33/110)
Have you lost interest in enjoyable things?	42.1% (24/57)	34.0% (18/53)	38.2% (42/110)
Have you experienced fits/jerks?	1.8% (1/57)	1.9% (1/53)	1.8% (2/110)
Have your arms or legs been shaky?	3.5% (2/57)	11.3% (6/53)	7.3% (8/110)
Have you had restless legs?	8.8% (5/57)	22.6% (12/53)	15.5% (17/110)
Have you been less interested in sex?	17.5% (10/57)	24.5% (13/53)	20.9% (23/110)
Have you found it difficult to enjoy sex?	15.8% (9/57)	13.2% (7/53)	14.5% (16/110)
Have you been unable to reach orgasm?	24.6% (14/57)	18.9% (10/53)	21.8% (24/110)
Have the areas around your nipple been sore and/or swollen?	3.5% (2/57)	0.0% (0/53)	1.8% (2/110)
Have you experienced any side effect at all including but not limited to those you've already answered?	19.3% (11/57)	7.5% (4/53)	13.6% (15/110)

Each row of the table includes only those subjects with a response of Yes or No.

Table 2: Side Effects Reported by Subjects at Week 8				
	Immediate Treatment	Delayed Treatment	Total	
Have you felt weak?	18.0% (11/61)	11.7% (7/60)	14.9% (18/121)	
Have you felt drugged or like a zombie?	8.2% (5/61)	3.3% (2/60)	5.8% (7/121)	
Have you been sweating more than usual?	6.6% (4/61)	10.0% (6/60)	8.3% (10/121)	
Have you felt tired during the day?	63.9% (39/61)	63.3% (38/60)	63.6% (77/121)	
Have you had difficulty staying awake during the day?	21.3% (13/61)	28.3% (17/60)	24.8% (30/121)	
Have you had difficulties waking up fresh in the morning?	65.6% (40/61)	61.7% (37/60)	63.6% (77/121)	
Have you gained weight?	26.2% (16/61)	20.0% (12/60)	23.1% (28/121)	
Do you think some foods taste different/odd?	0.0% (0/61)	15.0% (9/60)	7.4% (9/121)	
Have you felt more hungry than usual?	18.0% (11/61)	13.3% (8/60)	15.7% (19/121)	

Have you been more thirsty than usual?	18.0% (11/61)	20.0% (12/60)	19.0% (23/121)
Have your stools been hard or difficult to pass?	26.2% (16/61)	25.0% (15/60)	25.6% (31/121)
Have you needed to go to the toilet often?	18.0% (11/61)	10.0% (6/60)	14.0% (17/121)
Has your skin been more sensitive to the sun?	0.0% (0/61)	3.3% (2/60)	1.7% (2/121)
Have you noticed any areas of darker skin?	3.3% (2/61)	5.0% (3/60)	4.1% (5/121)
Are you experiencing any skin irritation where you place the Fisher Wallace device?	4.9% (3/61)	1.7% (1/60)	3.3% (4/121)
Do you have diabetes?	1.6% (1/61)	6.7% (4/60)	4.1% (5/121)
Have you been told that your blood sugar levels are high?	6.6% (4/61)	3.3% (2/60)	5.0% (6/121)
Have you noticed a change in your blood sugar levels?	1.6% (1/61)	0.0% (0/60)	0.8% (1/121)
Has your vision been blurry?	13.1% (8/61)	18.3% (11/60)	15.7% (19/121)
Have your eyes felt dry and gritty?	26.2% (16/61)	20.0% (12/60)	23.1% (28/121)
Are you experiencing any unusual eyestrain or headaches?	16.4% (10/61)	21.7% (13/60)	19.0% (23/121)

Have you found that your words dont come out clearly?	8.2% (5/61)	5.0% (3/60)	6.6% (8/121)
Have you found it difficult to swallow?	0.0% (0/61)	1.7% (1/60)	0.8% (1/121)
Have you felt anxious?	37.7% (23/61)	33.3% (20/60)	35.5% (43/121)
Have you felt agitated?	29.5% (18/61)	26.7% (16/60)	28.1% (34/121)
Have you lost interest in enjoyable things?	37.7% (23/61)	31.7% (19/60)	34.7% (42/121)
Have you experienced fits/jerks?	3.3% (2/61)	1.7% (1/60)	2.5% (3/121)
Have your arms or legs been shaky?	1.6% (1/61)	1.7% (1/60)	1.7% (2/121)
Have you had restless legs?	8.2% (5/61)	11.7% (7/60)	9.9% (12/121)
Have you been less interested in sex?	19.7% (12/61)	21.7% (13/60)	20.7% (25/121)
Have you found it difficult to enjoy sex?	14.8% (9/61)	13.3% (8/60)	14.0% (17/121)
Have you been unable to reach orgasm?	9.8% (6/61)	15.0% (9/60)	12.4% (15/121)
Have the areas around your nipple been sore and/or swollen?	0.0% (0/61)	3.3% (2/60)	1.7% (2/121)
Have you experienced any side effect at all including but not limited to those you've already answered?	18.0% (11/61)	8.3% (5/60)	13.2% (16/121)
Each row of the table includes only those subjects with a response of Yes or No.			

Subjects in the Immediate Treatment arm experienced a decrease of 10.4 points in BDI-II scores. This decrease of greater than ten points is indicative of antidepressant effectiveness.

More than 40% of the patients had a decrease of 50% in BDI-II or more. Due to high levels of placebo response, the between group difference in BDI-II change was -0.8 (p = 0.496). Significantly, and despite the fairly large drop in BDI-II during the first four weeks in the sham arm, the switch to active treatment was associated with additional improvement (BDI-II decrease from week 4 to 8 of 3.6 points) beyond what they had experienced during the first four weeks, while the Immediate Treatment arm only showed minimal additional improvement in this period (BDI-II decrease of 0.6 points, p < 0.01), representing an improvement of more than 15% from BDI-II scores from the end of the sham period. Thus, the data demonstrate the effectiveness of the FW-200 in treating depression.

# 5 BENEFITS AND RISKS OF THE INVESTIGATIONAL DEVICE, CLINICAL PROCEDURE AND CLINICAL INVESTIGATION

# 5.1 ANTICIPATED CLINICAL BENEFIT

Participation in this study may treat moderate to severe Major Depressive Disorder in adults (ages 21-65).

Knowledge gained from this study may enable future patients to benefit from CES.

#### 5.2 POTENTIAL ANTICIPATED ADVERSE EVENTS

Potential anticipated adverse events are those that may occur in association with a CES treatment, including those AEs listed below that are known risks from clinical experience/use of the FW-200 and similar CES devices (*Federal Register :: Neurological Devices; Reclassification of Cranial Electrotherapy Stimulator Devices Intended To Treat Anxiety and/or Insomnia; Effective Date of Requirement for Premarket Approval for Cranial Electrotherapy Stimulator Devices Intended To Treat Devices Intended To Treat Devices Intended To Treat Anxiety and/or Insomnia; Effective Date of Requirement for Premarket Approval for Cranial Electrotherapy Stimulator Devices Intended To Treat Depression, n.d.).* 

Risks associated with CES and CES devices include:

- Skin irritation
- Headaches
- Dizziness
- Electrical shocks and burns

The FW-200 is contraindicated for patients with the following:

- Demand or sensing type pacemakers, or any other form of implanted electronics
- Known heart disease
- A poor reaction to the idea of electrical stimulation of any kind
- Skin irritation around either electrode site
- The device should not be used around the Carotid sinus

CES-MDD	Version 5.0
FW-200-05	08-Jun-2022

As stated in the CES-MDD User Guide section, the FW-200 should not be used on the throat, neck or eyes. Subjects should avoid using the device near areas of the body where there is embedded shrapnel or metal plates. There is no danger to subjects using the device who have had dental fillings.

Subjects may experience skin irritation at the site of sponge electrode placement, especially if the sponges deteriorate or if contact is made between the skin and the metal part of the sponge receptacle, or if the sponges are not thoroughly wet before each use. Please refer to the CES-MDD User Guide for more information.

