# 7.2 SUBJECTS

# 7.2.1 Inclusion Criteria for Subject Selection

Subjects will need to meet all the following inclusion criteria:

- 1. Age 21-65 years and a resident of the United States of America
- 2. Meets DSM-5 diagnostic criteria for moderate to severe Major Depressive Disorder
- 3. Baseline BDI-II score between 20 and 63, inclusive (in moderate to severe range)
- 4. Able to receive packages to their home via UPS/FedEx/USPS or other delivery service
- 5. Willing and able to send and receive study related text messages on an internet capable mobile device throughout the duration of the study
- 6. Owns and uses a personal, verifiable email address
- 7. Able to commit to two (2) 20-minute treatment sessions per day for 4 weeks, one treatment upon waking for the day and one treatment before going to bed
- 8. Willing to abstain from use of recreational drugs, hypnotics, steroids, and/or marijuana products through study completion
- Willingness to not initiate treatment for a mental health issue during the course of the study 10.
   Fluent in English

Version 5.0 08-Jun-2022

- 11. Sexually active females of childbearing potential willing to commit to practicing at least one or more of the following methods of contraception during the study: intrauterine device (IUD), barrier method in combination with a spermicide, oral/hormonal contraception, or abstinence
- 12. In the opinion of the investigator, able to comply with study requirements and complete the study

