#### 7.2.2 Exclusion Criteria for Subject Selection

Subjects will not meet any of the following exclusion criteria:

- 1. History of suicide attempt or active suicidal ideation with plan or intent in the past 30 days
- 2. In the opinion of the investigator, considered high risk of suicide
- 3. Previous hospitalization or institutionalization for mental health condition within one year of study entry
- 4. Underwent electronic brain stimulation or neuromodulation within the past one year, including CES, transcranial magnetic stimulation, electroconvulsive therapy, and deep brain stimulation
- 5. Modification of prescription medications that affect the nervous system including those for mental health issues within 30 days of study entry. A patient who has been on a stable dose of prescription medications that affect the nervous system or being used for a mental health issue for at least 30 days prior to study entry and are not expected to modify their medication while on the trial are allowed to participate.
- 6. Use of recreational drugs, hypnotics, steroids, and/or marijuana products in the past 30 days
- 7. History of alcohol use disorder or other substance use disorder in the past 12 months
- 8. Females currently pregnant or planning to conceive during study participation, or unwilling to comply with birth control requirements
- 9. Known history of heart disease
- 10. Known history of trigeminal neuralgia
- 11. Implanted with an electronic device such as a defibrillator, deep brain stimulator, or pacemaker
- 12. Unstable medical condition defined as any condition requiring hospitalization or change in treatment in the prior 30 days
- 13. Legally blind and/or deaf and without in-home care service to assist with study participation
- 14. Meets M.I.N.I. assessment criteria for, or has been diagnosed with, any of the following: Bipolar I disorder, bipolar II disorder, other specified bipolar and related disorder, panic disorder, agoraphobia, social anxiety disorder (social phobia), obsessive-compulsive disorder, posttraumatic stress disorder, alcohol use disorder in the past 12 months, substance use disorder (non-alcohol) in the past 12

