months, any psychotic disorder (e.g., schizophrenia, schizoaffective disorder), major depressive disorder with psychotic features, anorexia nervosa, bulimia nervosa, binge-eating disorder, generalized anxiety disorder, any cognitive or developmental disorder (e.g., autism, Down's Syndrome), any personality disorder or psychiatric disorder that may interfere with study participation

- 15. Current participation in another investigational study or participated in an investigational study within the past 30 days
- 16. In the opinion of the investigator, may not be able to comply with study requirements and complete the study
- 17. Any employee, family member, or personal associate of the Sponsor or their designees conducting the study

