## 7.3.3.1 Informed Consent

The investigative team will introduce the potential participant to the clinical investigation by explaining the protocol including the study objectives, procedures, and participation requirements.

If the potential participant is interested in participating, the study staff will review the informed consent form. This will include describing the clinical investigation, potential discomforts, risks, and benefits of participation. The potential subject will have sufficient time to decide whether they wish to participate in this clinical investigation.

Any queries that the potential participant may have regarding this clinical investigation will be addressed appropriately by the investigative team. Potential subjects will be instructed that they are free to obtain further information from the Principal Investigator and investigative team at any time and that they are free to withdraw their consent and to discontinue their participation in the clinical investigation at any time without prejudice.

If the potential participant is willing to participate in the clinical investigation, he/she must read, understand and sign the informed consent form. The informed consent form will be sent to the potential subject electronically via a validated signature program such as DocuSign. The potential subject will be asked to complete the electronic signature of the form. The Principal Investigator or designee who conducted the informed consent discussion will also sign. A copy of the signed consent will be provided to the subject electronically. Written or electronic informed consent from the subject must be obtained before any clinical investigation related procedures are performed.

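### Two of the four patient-level contraindications in Section 5.2 are missing from the eligibility criteria; current skin irritation at an electrode site is the one that matters in practice

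*Combined protocol and SAP*

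**What the plan says.** Section 5.2 opens its list with "The FW-200 is contraindicated for patients with the following" and gives five bullets. Four describe a patient: implanted electronics, known heart disease, "A poor reaction to the idea of electrical stimulation of any kind", and "Skin irritation around either electrode site". The fifth says where not to use the device (the carotid sinus).

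Section 7.2.2 carries over two of the four: "Known history of heart disease" (exclusion 9) and "Implanted with an electronic device such as a defibrillator, deep brain stimulator, or pacemaker" (exclusion 11). Nothing in Sections 7.2.1 or 7.2.2 names the other two, and no criterion excludes device contraindications in general.

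Under Sections 7.1.1 and 7.3.5, a subject who has the diagnosis and meets the written criteria is prescribed a device. Randomisation (7.3.6) and shipment (7.3.6.1) follow. Live training takes place once the device has arrived (7.3.7), and first use is fixed as the day after training (7.1.1, 7.3.8).

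**The concern.** The safety statement and the eligibility rule disagree. A person with irritated skin where the sponge will sit can pass every written criterion, be randomised, and be asked to apply the device to that skin twice a day for four weeks, or 2 × 28 = 56 sessions. Skin irritation is the first device risk that Section 5.2 lists. The trial is fully remote, and no pre-screen, interview or training step names a check of the electrode site.

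What is at stake is patient safety and the protocol's consistency with itself. Whether a stated contraindication is applied should not depend on an individual clinician remembering Section 5.2.

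**Working it through.** No figure in the plan needs reproducing here. The check is a comparison of texts.

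**Step 1. Match each contraindication to the criteria.**

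| Section 5.2 item | Patient-level? | Criterion that names it |
|---|---|---|
| Implanted electronics | Yes | Exclusion 11 |
| Known heart disease | Yes | Exclusion 9 |
| Poor reaction to the idea of stimulation | Yes | None |
| Skin irritation at an electrode site | Yes | None |
| Carotid sinus | No, placement rule | Not applicable |

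Criteria searched: 12 + 17 = 29. Patient-level items: 5 − 1 = 4. Named: 2. Not named: 4 − 2 = 2.

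**Step 2. What else might stop a subject averse to stimulation?** Consent includes "describing the clinical investigation, potential discomforts, risks, and benefits of participation" (7.3.3.1). Inclusion 7 requires that the subject be "Able to commit to two (2) 20-minute treatment sessions per day for 4 weeks". Inclusion 12 and exclusion 16 cover expected compliance; exclusion 16 reads "In the opinion of the investigator, may not be able to comply with study requirements and complete the study". Few averse people would pass all of these.

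**Step 3. What else might stop a subject with irritated skin?**
- Medical history and medications are collected at pre-screening (7.1.1, 7.3.2), and the clinician reviews the reported data before prescribing (7.3.5). A skin problem may surface, but no criterion makes it disqualifying.
- Exclusion 6 and inclusion 8 bar steroids without naming a route, which may catch some treated skin disease.
- Exclusion 12 requires hospitalisation or a change of treatment in the prior 30 days.
- Staff are trained on the protocol (5.3) and could apply Section 5.2 on their own judgement. Section 7.3.5 lists psychiatric exclusions and points to the written criteria, not to 5.2.

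What remains is irritation that is untreated, or on stable non-steroid treatment, and that no clinician chooses to act on.

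**Step 4. What protects that subject after randomisation?** Staff review the User Guide with the subject, who confirms understanding before independent use (3.8). During treatment there are daily health reports (7.1.1, 7.3.8), staff review of entered data for safety (9.1.1), and contact after any recorded adverse event, with a temporary halt or discontinuation among the recorded actions (15.2.1). These limit harm, but they come after shipment and are not an eligibility gate.

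**Step 5. Context from the prior trial (4.2, Tables 1 and 2).** Irritation where the device is placed:
- Week 4: immediate (active) arm 4/57 = 7.0%, delayed (sham) arm 2/53 = 3.8%, together 6/110 = 5.5%.
- Week 8: 3/61 = 4.9% and 1/60 = 1.7%, together 4/121 = 3.3%.

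No serious adverse events were reported. These are rates during use, not at screening.

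**The case against.** The strongest reply is that the Section 5.2 list mixes patient conditions with rules of use. It ends with the carotid sinus instruction and is followed by further User Guide rules. Local irritation can be transient, so it could be read as something to check at each use, controlled by labelling and training as Section 5.3 says. On that reading there is no conflict. The reading does not survive the lead-in, which speaks of patients for whom the device is contraindicated, or the fact that the protocol turned two items of the same list into exclusions.

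Other parts of the reply do stand:
- A reader might infer that nothing in the plan would stop a subject with irritated skin. The documents do not support that. History and medication review, the steroid bar, exclusion 12 and an individual prescription by a trained clinician each catch some cases.
- Half of the count has little practical weight, because aversion is largely filtered before randomisation.
- The User Guide may carry the skin warning. It is not among the documents, so this cannot be settled. Even if it does, its live review falls after the device has arrived.
- A pre-screen answer given at least 14 days before baseline says little about a transient condition at first use. The interview check therefore has to be the working gate.
- Deferring first use after randomisation has a price. Subjects withdrawn after receiving a device are not replaced (7.3.15.1) and stay in the intent-to-treat analysis (8.1), so any deferral needs a cap.

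**Conclusion.** The point holds as a minor safety alignment that is cheap to make. Two of four patient-level contraindications are absent from all 29 criteria. The skin item is a real, partly covered gap; the aversion item is worth adding mainly for consistency.

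A reader might apply the prior trial's 7.0% to this trial and expect about 250 × 4/57 = 17.5 affected subjects. That is not supported: the 4/57 describes irritation reported during treatment, and the documents give no prevalence at entry. A reader might also infer a threat to the primary result. None is claimed for alpha, power, sample size or inference.

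The conclusion rests on two assumptions: that Section 5.2 states current contraindications, and that eligibility is decided on the written criteria, as Section 7.3.5 describes. Likely harm is local and, given daily reporting, can be stopped early.

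**What to change.** 1. Add two exclusions to Section 7.2.2 and the synopsis: current irritation or broken skin at either electrode site, and a poor reaction to the idea of electrical stimulation.
2. Ask both in the electronic pre-screen. Treat a positive skin answer there as a flag for re-checking.
3. Have the clinician confirm both at the Section 7.3.5 interview, before randomisation.
4. Optional: add a skin check at live training (7.3.7), with a short deferral of first use up to a cap set by the clinical team. This needs one amended sentence each in 7.1.1 and 7.3.8. Day 0 is the first day of treatment (7.3.1), so the assessment windows move with it. Analyse any subject who never starts as randomised.

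Deleting the two items from Section 5.2 would also remove the contradiction, but it could put the protocol at odds with the User Guide, so adding the criteria is safer.

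Cost of steps 1 to 3: two lines in each of two places, two yes/no questions and one interview confirmation, with a few more screen failures. Step 4 adds, rarely, a slightly longer gap between baseline BDI-II and Day 0, or a randomised subject who never starts and is not replaced.
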